1.6 DCE and DSC-MRI

The measurement of perfusion in the brain using MRI is now commonplace and traces its origin to the seminal paper by Ostergaard et al.[39]. This technique is now referred to as dynamic susceptibility contrast (DSC) and relies on measuring the T2* signal changes that occur in the brain as a bolus of contrast material dynamically passes through the capillary circulation. DSC methods have since proved valuable in the diagnosis of stroke and brain tumors and are routinely used in our radiology practice. The mathematical model that describes DSC assumes that the blood brain barrier (BBB) is intact, but this assumption does not often hold in enhancing high-grade glial tumors, which are often supplied by leaky neo-vascularity. The leakage of contrast into the extracellular space causes changes in the T1 signal [40], which can invalidate uncorrected DSC measurements in tumors. Several methods, such as DCE, have been proposed to correct for this leakage [40, 41], some of which rely on a 2-compartment pharmacokinetic model that can estimate the vascular transfer constant (K_{trans})[41]. K_{trans} is a parameter that describes the ability of contrast to move from the intravascular compartment to the extracellular compartment (the 2 compartments in the model) and thus provides a quantitative measure of the degree of BBB leakage. Law et al. used this model to measure K_{trans} and cerebral blood volume (CBV)

[figure not shown]

Figure 3. Perfusion measurements in patients with GBM. See text for details.

in 74 patients with glial tumors and demonstrated that the combination of both measures

provided the best discriminator for high-grade gliomas, thus providing validation for this model[42].

We implemented a modified version of the Johnson model[41] and applied it to several patients with high-grade gliomas as illustrated in Figure 3. Figure 3A is a T1-

weighted post contrast image of the tumor, seen as a ring enhancing mass on the left side of the brain (right side of the image). Figure 3B is the same slice in a T2*-weighted image that is used to measure the signal change with the passage of a bolus of contrast material. Several regions of interest (ROI) are drawn on this image where measurements were made. The red ROI was placed in an area of relatively large BBB leakage, the blue ROI in an area of less leakage, and the green ROI in normal white matter. Figure 3C demonstrates the normalized tissue signal curves during the bolus tracking period that correspond to the drawn ROIs. The large signal drop seen centered at time frame 15 is taken at the peak of the contrast bolus transition. The depth and recovery of the signal during and after the bolus passage provides information on the degree of BBB leakage and on the value of Ktrans. In the normal white matter (green) the signal nearly recovers fully to its original value, consistent with the residual contrast left in the blood stream after the passage of the primary bolus. In the enhancing portion of the tumor (red and blue) the signal has a larger drop and does not fully recover providing us with estimates of the Ktrans.

As part of the Monteris study on the adult tumor population we have employed another method to measure the break down of the BBB called dynamic contrast-enhanced MRI (DCE-MRI). DCE-MRI is another common method used to evaluate for permeability of blood vessels in the brain[8]. Similar to DSC-MRI, DCE-MRI consists of injection of an MRI contrast agent followed by multiple T1-weighted images to assess the leakage of this agent into the extracellular space over several minutes. Again, the rate of pooling of the contrast agent is then used to quantify the degree of BBB permeability. Figure 4 demonstrates results from our recent study in 4 sample patients. The horizontal axis represents the number of days post-surgery with each time point representing an MRI

[figure not shown]

Figure 4: Examples of longitudinal Ktrans measurements in tumor patients follow the monteris procedure using the DCE method. More detail provided in the text

1.7 Biomarkers of BBB Disruption

The coagulative necrosis and BBB disruption induced by MLA share several parallels with classical brain injuries (e.g. traumatic, surgical, ischemic, or pathologic brain damage), albeit in a more controlled setting. Several serum biomarkers have been identified, and in some cases extensively validated, in large number of patients with various forms of brain injuries. The compromised BBB after brain injuries allows CNS-specific factors released by damaged CNS cells to escape into the peripheral circulation where they can be detected using highly sensitive and specific detection techniques such as ultrasensitive ELISA, antibody arrays and HPLC/mass spectroscopy. The temporal profile of serum levels of these brain-specific factors (e.g. S100B, GFAP, brain-specific enolase or BSE) can provide information about the duration and degree of BBB disruption[43-53], irrespective of the type of brain injuries.

We will measure serum levels of these 4 brain-specific factors (S100B, GFAP, and BSE) immediately before and after MLA and then during the 6 weeks post-MLA, using ultrasensitive ELISA. If MLA results in sustained BBB disruption, we expect that the level of at least one of these biomarkers will increase precipitously soon after MLA and well above that caused by recurrent GBM, and that the increase will persist for several days to weeks. Antibody microarray can substitute ELISA if higher detection sensitivity is needed. We chose these biomarkers as they have previously been validated in brain trauma, recognizing that other brain specific factors may be more reliable.

1.9 Study Rationale

By employing a combination of advanced MRI techniques and correlative serum biomarkers of BBB disruption, we plan to develop a powerful, first of its kind clinical algorithm in pediatrics whereby we can measure and identify the window of maximal BBB disruption post MLA to 1) allow for an alternative to surgery in incompletely resected tumors, 2) allow for optimal chemotherapeutic dosing to achieve the greatest benefits and the least systemic side effects and 3) distinguish subsequent tumor progression from long-term MLA treatment effects. Preliminary data in adult imaging studies have shown that the BBB disruption lasts for several weeks following treatment before returning to a low baseline. This pilot therapeutic study will provide preliminary validation in pediatric patients.

Although we have a large armamentarium of cytotoxic drugs with potential activity against brain tumors, the vast majority has poor CNS penetration limiting their usefulness. Our proposed use of MLA to achieve both cytoreduction and increased permeability of the peritumoral BBB has the potential to be practice changing and will allow us to test many drugs that have not shown promise due to poor BBB penetration. The innovative algorithm

to detect and measure MLA-induced peritumoral BBB compromise may also be applied using other treatments.

Recent work has collectively demonstrated striking immune dysregulation in patients with GBM, including T cell lymphopenia and anergy, cytokine dysregulation, and increased regulatory T cell (T_{reg}) populations among others, which reflect immunologic compromise and functional impairment[54-57]. However, a growing list of potential tumor antigens has been identified, suggesting that tumor-specific recognition by immune cells may be biologically relevant and therapeutically exploitable[55, 58]. Therefore, given the immune dysfunction characterized in GBM patients, approaches that potentiate the anti-glioma immune response are particularly exciting. A priori, because the immune system has evolved to recognize a tremendous diversity of antigenic epitopes in vertebrates, immune-potentiating efforts – with MLA being one potential approach – may be especially effective at targeting the heterogeneity that defines GBM.

2.0 OBJECTIVES

2.1 Primary Objectives

1. To determine progression-free survival (PFS) and overall survival (OS) of patients with new diagnosis glioma who are candidates for MLA (Arm A).
2. To determine 6-month progression-free survival (6PFS) in patients who receive doxorubicin immediately following MLA and low-dose etoposide as maintenance therapy in patients who are candidates for MLA with any type relapsed malignant brain tumors (Arm B).
3. To evaluate quality of life (QOL) using Karnofsky or Lansky performance status in patients following MLA and in patients who receive doxorubicin and maintenance etoposide after MLA.

2.2 Secondary Objectives

1. To determine MR imaging correlates of peritumoral BBB disruption after MLA.
2. To identify serum biomarkers of peritumoral BBB disruption after MLA, which can be used to establish peritumoral permeability scores.
3. To determine the predictive value of the peritumoral permeability score for patient outcome as measured by 6PFS rate.

2.3 Exploratory Objective

To determine the effects of MLA treatment on patient's tumor-specific immune responses

and immunological correlates.

3.0 PATIENT SELECTION

3.1 Inclusion Criteria – Arm A

1. Presumed pediatric gliomas (grades I-IV) on MRI that are determined to be candidates for MLA by the treating neurosurgeon.
2. Age 3 to \leq 21
3. Karnofsky/Lansky performance status \geq 60%, see Appendix 1.

3.2 Inclusion Criteria – Arm B

1. Recurrent pediatric brain tumors determined candidates for MLA as determined by the treating neurosurgeon.
2. Unequivocal evidence of tumor progression by MRI (see Section 12).
3. There must be an interval of at least 12 weeks from the completion of radiotherapy to study registration except if there is unequivocal evidence for tumor recurrence per RANO criteria (see Section 12). When the interval is less than 12 weeks from the completion of radiotherapy, the use of PET scan is allowed to differentiate between evidence of tumor recurrence and pseudoprogression.
4. Recurrent lesions with dimension and contour that are determined by the treating neurosurgeon to be appropriate for MLA.
5. Age 3 to \leq 21
6. Karnofsky/Lansky performance status \geq 60%, see Appendix 1.
7. Adequate cardiac function as determined by a shortening fraction \geq 27% or left ventricular ejection fraction \geq 50% by echocardiogram within the past 1 year prior to registration.
8. Prior anthracycline therapy does not exceed 200 mg/m² total cumulative dose.
9. Adequate bone marrow and hepatic function as defined below (must be within 7 days of MLA):
 - a. Absolute neutrophil count (ANC) \geq 1000/mcl (G-CSF is allowed)
 - b. Platelets \geq 100 K/cumm
 - c. Hemoglobin \geq 9 g/dL (pRBC transfusion +/- ESA are allowed)
 - d. ALT \leq 3 x ULN

- e. $AST \leq 3 \times ULN$
 - f. $ALP \leq 3 \times ULN$. If ALP is $> 3 \times ULN$, GGT must be checked and be $\leq 3 \times ULN$.
 - g. $Bilirubin \leq 2 \times ULN$
10. At the time of registration, patient must have recovered from the toxic effects of prior therapy to no more than grade 1 toxicity.
 11. At the time of registration, patient must be at least 4 weeks from other prior cytotoxic chemotherapy.
 12. Women of childbearing potential and men must agree to use adequate contraception (hormonal or barrier method of birth control, abstinence) prior to study entry and for the duration of study participation. Should a woman become pregnant or suspect she is pregnant while participating in this study, she must inform her treating physician immediately.
 13. Ability to understand and willingness to sign an IRB approved written informed consent document (or that of legally authorized representative, if applicable).

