The ideal cytotoxic drugs for the purpose of this proposal should have potent activities against malignant cell lines *in vitro*, and *in vivo* activity that is limited by blood brain barrier function. Doxorubicin has been shown to kill a large number of high grade glioma cell lines *in vitro* [18, 32]. However, it has poor CNS penetration and has not been used extensively in CNS tumors. Doxorubicin and other anthracyclines induce cytotoxicity through intercalating between DNA base pairs, thereby interfering with strand elongation by DNA and RNA polymerase. Doxorubicin also affects topoisomerase II, which creates temporary double-strand DNA breaks during DNA replication. Doxorubicin stabilizes the DNA-topoII complex leading to double-strand DNA breaks and cell death. Doxorubicin has a wide volume of distribution with tissue levels proportional to the DNA content of the tissue. Doxorubicin is 75% bound to plasma proteins. Doxorubicin is mostly metabolized in the liver and eliminated mainly as glucuronide or hydroxylated conjugates in the bile and feces. The half-life of doxorubicin is 1 to 3 hours.

Maintenance chemotherapy using low-dose etoposide (21-day cycles) will be given following the course of doxorubicin. Low-dose etoposide has been found effective in treating relapsed brain tumor patients by extending PFS [33-36]. Etoposide is a topoisomerase II inhibitor and has been shown to inhibit tumor cell proliferation at high doses and to function as an anti-angiogenic agent when administered in low daily doses (metronomic chemotherapy) [37]. *In vitro* and pre-clinical studies demonstrate that low dose daily etoposide inhibits secretion of angiogenic factors, proliferation of endothelial cells, and endothelial tube formation [37]. This agent has been well tolerated in pediatric patients when given as low-dose, metronomic therapy.

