3.4 Exclusion Criteria – Arm B

1. Prior treatment with bevacizumab within 12 weeks of study entry.
2. Previous treatment with complete cumulative doses of daunorubicin, idarubicin, and/or other anthracyclines and anthracenediones that is equivalent to a total dose of $> 200 \text{ mg/m}^2$ doxorubicin.
3. More than 2 prior relapses (not counting the current relapse being treated on this study).
4. Currently receiving any other investigational agents that are intended as treatments of the relapsed tumor.

5. Multi-focal or metastatic disease.
6. A history of allergic reactions attributed to compounds of similar chemical or biologic composition to doxorubicin or other agents used in the study.
7. Uncontrolled intercurrent illness including, but not limited to, ongoing or active infection, symptomatic congestive heart failure, unstable angina pectoris, cardiac arrhythmia, recent heart attack within the previous 12 months or severe heart problems, or psychiatric illness/social situations that would limit compliance with study requirements.
8. Pregnant and/or breastfeeding. Premenopausal women must have a negative serum or urine pregnancy test within 14 days of study entry.
9. Inability to undergo MRI due to personal or medical reasons.
10. Known history of HIV or autoimmune diseases requiring immunosuppressant drugs.

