10.2 Arm B Study Calendar

	B/L ¹	MLA	3 Days Post-MLA	Wk 1 ⁴	Wk 2 ⁴	Wk 3 ⁴	Wk 4 ⁴	Wk 5 ⁴	Wk 6 ⁴	Monthly ⁵	F/U ¹⁰
Informed consent	X										
Medical history	X									X	
Physical exam incl. wt	X			X	X	X	X	X	X	X	X ¹⁵
Karnofsky/Lansky	X			X	X	X	X	X	X	X	X ¹⁵
CBC	X			X	X	X	X	X	X	X	
CMP	X			X			X			X	
Urine or serum β HCG	X ¹²										
Echocardiogram	X ²										
MRI with DCE/DSC	X ¹⁴		X		X ¹¹					X ^{5,6}	
Biopsy		X ¹⁴									
Blood to measure brain-specific factors (Section 9.2-9.4)		X ³	X	X ⁷	X ⁷	X ⁷	X ⁷	X ⁷	X ⁷	X ^{5,6}	
Doxorubicin ⁸				X	X	X	X	X	X		
Etoposide ¹³										X	
AE assessment ⁹		X	-----								X

1. No more than 21 days prior to MLA.

2. No more than 1 year prior to registration.

3. May be collected any time during the 3 days before or the day of the procedure until the start of the procedure.

4. +/- 3 days

5. +/- 7 days

6. Every 8 weeks for the first 2 years or until disease progression, whichever occurs first. To coincide with MRI. After progression, vital status and subsequent treatment will be recorded.

7. Same day as chemotherapy.

8. To begin approximately 7 days after MLA.

9. Through one year or off protocol

10. Patients will be followed every 6 months or at event occurrence for 5 years or until death, whichever occurs first.

11. To be obtained 2-4 weeks post-MLA

12. Females of childbearing potential

13. To be started at time of count recovery after the 6 weeks of treatment with doxorubicin has concluded.

14. Optional

15. +/- 2 weeks

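### Arm B accepts an echocardiogram up to a year old without requiring it to follow prior anthracycline, so a child can qualify on a test that predates the exposure

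*Combined protocol and SAP*

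**What the plan says.** Section 3.2 item 7 asks for a shortening fraction (SF) of at least 27% or an ejection fraction (EF) of at least 50% "by echocardiogram within the past 1 year prior to registration". Footnote 2 of the Arm B calendar (Section 10.2) sets the same limit, "No more than 1 year prior to registration", and the echocardiogram row is marked at baseline only.

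Three other items in Section 3.2 bear on prior treatment:
- Item 8: "Prior anthracycline therapy does not exceed 200 mg/m² total cumulative dose". Section 3.4 exclusion 2 restates the cap in doxorubicin equivalents and counts "daunorubicin, idarubicin, and/or other anthracyclines and anthracenediones".
- Item 11: at registration the "patient must be at least 4 weeks from other prior cytotoxic chemotherapy".
- Item 10: at registration the "patient must have recovered from the toxic effects of prior therapy to no more than grade 1 toxicity".

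Other entry tests are dated closely. Item 9 reads "Adequate bone marrow and hepatic function as defined below (must be within 7 days of MLA", and the calendar's general baseline window is 21 days before MLA.

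Section 5.4 gives doxorubicin 25 mg/m² weekly for 6 weeks. Section 6.0 advises omitting it for a week if EF falls below 50% or SF below 27%, and stopping it if the abnormality persists. That section expects little cardiac toxicity because study doxorubicin is low in dose and short in duration.

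**The concern.** The purpose of item 7 is to show adequate cardiac function before an anthracycline is given. It can do that only if the test reflects the heart as it is after earlier cardiotoxic treatment. As written, the order of the two events is left open: a normal echocardiogram, then months of anthracycline, then registration would satisfy every criterion.

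At stake is the safety of a child whose function has fallen without symptoms. On a new echocardiogram below both cut-offs, that child would fail item 7, and Section 6.0 would advise withholding doxorubicin. On the older result the same child is eligible and is scheduled for all six doses. The reassurance in Section 6.0 rests on the study dosing and does not address earlier exposure. Section 8.1.7 recognises that earlier cardiotoxic agents matter, but deals only with letting them clear from the circulation.

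**Working it through.** The plan states no figure to reproduce. The check is a comparison of windows and criteria.

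**Inputs**
- Oldest permitted echocardiogram: 365 days before registration (3.2 item 7; 10.2 footnote 2).
- Latest permitted prior cytotoxic chemotherapy: 4 weeks = 28 days before registration (3.2 item 11, read as covering anthracyclines).
- Prior anthracycline allowed: up to 200 mg/m² (3.2 item 8).
- Study doxorubicin: 25 mg/m² × 6 (5.4).
- Sample size: six patients in Arm B (5.1.2).

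**Step 1: span of exposure that can follow the qualifying test.** 365 − 28 = 337 days; 337 / 7 ≈ 48 weeks. If item 11 did not cover anthracyclines, the span would be longer, not shorter.

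**Step 2: can real treatment fit in that span?** Section 1.5 describes an ATRT regimen with 60 mg/m² of doxorubicin per course, 2 to 3 weeks apart. The number of courses is not given. Assuming three, the dose is 3 × 60 = 180 mg/m², within the cap of 200. The two intervals between courses take 4 to 6 weeks, well inside 48. Arm B is open to any type of relapsed malignant brain tumor (2.1), so such a child is not excluded by diagnosis.

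**Step 3: what the child then receives.** 6 × 25 = 150 mg/m². The calendar marks doxorubicin at weeks 1 to 6 and an echocardiogram at none of them, nor afterwards.

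**Step 4: does another criterion force a cardiac measurement after the prior exposure?**

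| Safeguard | What it does | Requires a post-exposure cardiac test? |
|---|---|---|
| 3.2 item 8 and 3.4 exclusion 2 | Cap prior dose at 200 mg/m² | No |
| 3.2 item 10 | Requires recovery to grade 1 or less | No; names no cardiac test |
| 3.4 exclusion 7 | Excludes symptomatic heart failure, arrhythmia and severe heart problems | No |
| Weekly examination (10.2) | May prompt a test | No |
| 6.0 cardiac rule | Acts on EF, SF or QTc | No; schedules none |

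**Step 5: who would be wrongly admitted?** Item 7 is met by either SF or EF. A fresh test showing both measures would therefore exclude only a child below both cut-offs.

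**The case against.** The strongest reply is that the protocol already controls prior exposure directly. The 200 mg/m² cap appears twice, known residual toxicity above grade 1 is a bar whatever the date of the echocardiogram, and clinical heart failure is excluded. What remains needs several things at once: anthracycline within the past year, a qualifying test before it and none used after it, a silent fall below both cut-offs, and unifocal recurrent disease suitable for MLA. Section 1.5 says of doxorubicin that "it has poor CNS penetration and has not been used extensively in CNS tumors". Nothing shows that the case occurs. All of this stands, and it is why the point is minor. It does not close the gap, because none of these safeguards obliges anyone to measure function after the exposure.

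A reader might infer more in three places, and the documents do not support it:
- **Total dose as the measure of the problem.** Adding 200 and 150 gives 350 mg/m² at the protocol's limits. That total follows from item 8 and the study dose and is the same whether the echocardiogram comes before or after the earlier drug.
- **Age of the echocardiogram, or absence of on-treatment tests, as the defect.** The remedy keeps the one-year limit, so an old test in an unexposed child remains acceptable. Any stated age at the sixth dose would also be unreliable, since Section 6.0 allows dosing delays. Whether to schedule tests during treatment is a design choice.
- **Bilirubin as a second established gap.** The calendar marks the CMP at weeks 1 and 4, so it coincides with 2 of 6 doxorubicin doses, while Section 6.0 adjusts doxorubicin on direct bilirubin. But Section 5.1.2 mentions routine bloods before chemotherapy without listing their content, and these may include bilirubin. The Section 6.0 rules are also advisory. This supports at most an optional, low-confidence suggestion.

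**Conclusion.** The concern holds as a minor, fixable gap in eligibility. The entry rule can admit a child who would fail its own cut-offs if tested after the earlier treatment. Up to 337 days (about 48 weeks) of permitted anthracycline exposure can follow the qualifying echocardiogram, and such a child would be scheduled for 150 mg/m² with no later scheduled cardiac test. The 48 weeks is a calendar window, not a frequency or a risk. The number affected is unknown, probably small, and at most six.

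The conclusion rests on reading item 11 as covering anthracyclines and on the calendar being the full schedule of required cardiac tests. It does not show that any child was harmed or wrongly enrolled. It does not touch the primary objectives in Section 2.1 or the analyses in Section 14.0.

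**What to change.** In Section 3.2 item 7 and in footnote 2 of the Section 10.2 calendar, keep the one-year limit and add: *and dated after the last prior dose of any anthracycline or anthracenedione*. These are the drug classes already counted in Section 3.4 exclusion 2. Children without such exposure are unaffected.

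The cost is one amendment to eligibility and calendar wording. The few children whose echocardiogram predates their last such dose would need a repeat of a non-invasive test the protocol already requires. That may bring a short delay, or exclusion if the new result fails item 7. Sample size, endpoints and analysis do not change.

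Optionally, the sponsor could state in Section 5.1.2 or the calendar whether the routine pre-chemotherapy bloods include bilirubin.
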